In the 9-month dog toxicity study, broadly distributed dermal-localized nodules were observed on all dogs at 15 and 30 mg/kg/day and one nodule was observed on one male dog at 6 mg/kg/day. The majority of nodules were identified microscopically as focal angiectasis, characterized as ectatic, blood-filled vessels with varying degrees of thrombosis that was occasionally associated with papillary endothelial hyperplasia; and one nodule in a high dose dog identified as benign hemangioma. The nodules ranged in size between 1 and 50 mm in diameter and appeared to slowly enlarge or remain static in size. The majority of nodules were persistent, but a few nodules were self-limiting while AKB-9778 dosing continued. The dermal nodules were observed to rapidly resolve upon drug withdrawal. In addition, largely GI tract-localized minimal to mild angiectasis was observed by microscopic examination at all dose levels in dog (at exposures 6- to 24-fold the human exposure at 15 mg BID) and not present in the vehicle control group. The vascular findings were not associated with any clinical observations, serum chemistry, or other microscopic changes. In the rat 6-month study, minimal focal angiectasis was observed by microscopic examination in the uterus with cervix of one high-dose rat (at higher AUC exposure than exposures assessed in dog) and was considered incidental. There were no skin nodules or GI-related findings in rat. In the 9-month monkey study, a solitary dermal nodule on the tail of one high dose animal was characterized as angiectasis with resolving thrombosis, and associated with AUC exposure higher than exposures assessed in dog. There were no GI-related findings in monkey. These observations suggest an increased sensitivity of the dog to vascular effects of AKB-9778. No unusual or unexpected dermal findings have been observed in clinical studies with AKB-9778. For guidance on assessment and monitoring of potential vascular effects refer to the Investigator's Brochure.

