9.3.1 Visit Windows

Plasma PK samples collected at 30 and 90 minutes after dosing of study medication on Day 1 and Month 6 should be collected within ± 10 minutes of the target time. If for any reason, the sampling time point for a given sample falls outside of the visit window, the sample must still be collected. For all samples; the exact time of sample collection will be recorded.

Blood pressure and heart rate evaluations performed must be conducted within ± 20 minutes of the designated time.

Subjects will only use AM syringes for dose administration in the morning and PM syringes for dose administration in the evening. Subjects should administer their daily doses around the same time every morning and evening, if possible. If a dose is missed, this dose should be skipped and the subject should maintain the morning and evening dosing schedule.

The Day 7 phone call must be conducted within ± 3 days.

Site visits scheduled for Months 1 through 12 should be conducted within 28 days times the study month number ± 3 days relative to the baseline visit (e.g. Month 1 visit window is 28 ± 3 days from Day 1, Month 2 visit window is 56 ± 3 days from Day 1, etc.).

Homecare nurse visits scheduled for Screening, Months 3, 6, 9 and 12 should be conducted within 1 week after the corresponding site visit. The Follow-up homecare visit occurs 4 weeks ± 3 days after the EOT visit at the site.

The fecal occult blood specimen collection and shipping to the Central Laboratory should be conducted by the subject within the week following the corresponding site visit.

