**Table 1: Visit Windows (Data Collected at All Monthly Visits – BP/HR, BCVA, chemistry)**

Visit	Target Day of the Visit	Visit Window (Days) for Analyses
Baseline	1	$\leq 1$
Week 4	29	15-42
Week 8	57	43-70
Week 12	85	71-98
Week 16	113	99-126
Week 20	141	127-154
Week 24	169	155-182

Week 28	197	183-210
Week 32	225	211-238
Week 36	253	239-266
Week 40	281	267-294
Week 44	309	295-322
Week 48	337	323-350

Note: All days are referenced to Day 1

**Table 2: Visit Windows (Data Collected at Months 3, 6, 9, 12 – Body System Assessments, Slit Lamp, IOP, Indirect Ophth, SD OCT, FP, OCT Angiography, ERG, Urinalysis, Fecal Occult Blood Test)**

Visit	Target Day of the Visit	Visit Window (Days) for Analyses
Baseline	1	< = 1
Week 12	85	82-126
Week 24	169	127-210
Week 36	253	211-294
Week 48	337	295-378

Note: All days are referenced to Day 1

Note: Urinalysis was not collected at Week 12, so it should not have a Week 12 Window; all other visit windows are as shown in the table.

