**Table 4: Visit Windows (Data Collected at Months 2, 4, 6, 8, 10, 12 – Hematology)**

Visit	Target Day of the Visit	Visit Window (Days) for Analyses
Baseline	1	<= 1
Week 8	57	29-84
Week 16	113	85-140
Week 24	169	141-196
Week 32	225	197-252
Week 40	281	253-308
Week 48	337	309-364

Note: All days are referenced to Day 1

When multiple observations are captured in a visit window, use the scheduled visit that matches the visit window in the analysis (e.g., if week 24 scheduled visit is in the week 24 window, use this visit for Week 24 analysis visit). If there is no scheduled visit that matches the visit window, the one closest to the target date of the visit will be used to represent the window. If two observations are equidistant from the target date, then the observation that is closer to the upper end of the window visit will be used.

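### SAP Table 2 has no follow-up row, so, read literally, an early discontinuer's off-drug follow-up body-system exam can be tabulated as a Week 12, 24, 36 or 48 result

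*SAP*

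**What the plan says.** **SAP 3.3, Table 2** is headed "Data Collected at Months 3, 6, 9, 12 – Body System Assessments" and goes on to list other assessments. Its rows are Baseline, Week 12 (target Day 85, Days 82-126), Week 24 (169, 127-210), Week 36 (253, 211-294) and Week 48 (337, 295-378). SAP 3.3 mentions a follow-up/exit visit at Week 52, but Tables 1 to 4 have no row for it.

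**Choice of record (SAP 3.3, below Table 4).** With several observations in a window, the first instruction is to "use the scheduled visit that matches the visit window in the analysis". Failing that, "the one closest to the target date of the visit will be used to represent the window". If two are equally distant, "then the observation that is closer to the upper end of the window visit will be used". SAP 7.3 sends recorded data to windows without setting post-treatment records apart.

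**Timing (Protocol 9.3.1).** The site schedule reads "Site visits scheduled for Months 1 through 12 should be conducted within 28 days times the study month number ± 3 days", counted from Day 1. The nurse exam may lag its site visit by up to 7 days. For the post-treatment exam the rule is: "The Follow-up homecare visit occurs 4 weeks ± 3 days after the EOT visit at the site". The follow-up visit includes a body-system assessment (Protocol 9.3.3.6). Early discontinuers enter follow-up unless they withdraw consent (Protocol 7.6). There is no dosing after the EOT visit (Protocol 9.3).

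**Related text.** SAP 5.5 defines the body-system shift at Weeks 12, 24, 36 and 48 only. Protocol 11.5 uses the worst record when a window holds more than one. SAP 1.1 reports no change from protocol.

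**The concern.** The Week 12 to Week 48 rows will be read as results on treatment. A day-based rule that does not exclude follow-up exams can fill such a row with an exam made about four weeks after dosing ended, in a subject who stopped early.

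The label matters because the body-system assessment includes direct inspection of the skin (Protocol 9.2.1). In the 9-month dog study, "The dermal nodules were observed to rapidly resolve upon drug withdrawal". Protocol 4.4.1 says it is unknown whether vascular ectasias will appear with longer human dosing. If human lesions also regressed off drug, a normal follow-up exam could stand in the table where the EOT exam had shown a finding.

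**Working it through.** **Reproducing the windows.** Target = 28 × month + 1; window = target − 42 to target + 41.
- Month 6: 169, Days 127-210
- Month 9: 253, Days 211-294
- Month 12: 337, Days 295-378

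All three match Table 2. For Month 3 the rule gives 85 and Days 43-126, whereas Table 2 prints 82-126. The printed limit is used below, so Days 2-81 have no row.

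**Base case.** Let d be the EOT day, from 2 to 333 (332 possible early days). The EOT exam is on day d and the follow-up exam on d + 28. Earlier scheduled exams were done, and an early EOT does not count as the Week 48 visit.

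**Follow-up exam is the only record.** This occurs when d + 28 falls in a window that starts after d. With lower limit L, d runs from L − 28 to L − 1, which is 28 days per window: 54-81 (Week 12), 99-126 (Week 24), 183-210 (Week 36), 267-294 (Week 48). Total 4 × 28 = 112.

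**Follow-up exam displaces the EOT exam.** Both lie in one window with target T and no matching scheduled exam. The follow-up exam wins if |d + 28 − T| ≤ |d − T|, that is, d ≤ T − 14. The EOT days are 127-155, 211-239 and 295-323, 29 per window. In Week 12, d would have to be at least 82 and at most 71, so there are none. Total 3 × 29 = 87. Two checks: for d = 141 the follow-up is on Day 169, 0 days from target against 28 for the EOT exam; for d = 155 both are 14 days away and the tie rule takes the later one.

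| Result for the follow-up exam | EOT days | Count |
|---|---|---|
| Only record in a Week 12-48 window | 54-81, 99-126, 183-210, 267-294 | 112 |
| Displaces the EOT exam | 127-155, 211-239, 295-323 | 87 |
| Falls in no window | 2-53 | 52 |
| Loses to the matching scheduled exam | 86-98, 170-182, 254-266 | 39 |
| Loses to a closer EOT exam | 82-85, 156-169, 240-253, 324-333 | 42 |
| Total | 2-333 | 332 |

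So 112 + 87 = 199 of 332 days (60%) put an off-drug exam in an on-treatment row. On the 112 days the EOT exam is not tabulated either: it falls before Day 82 or loses to the scheduled exam of the preceding window.

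**Timing variants.** The EOT nurse exam was set 0 or 7 days after the site visit, the follow-up at +25, +28 or +31 days, and an early EOT was counted or not counted as Week 48.
- Lowest: 7-day lag, +25, counted as Week 48: 72 + 68 = 140 (42%).
- Highest: no lag, +31, not counted: 124 + 81 = 205 (62%).
- Displacement alone: 54 to 102 days (16-31%).
- Base case with an early EOT counted as Week 48: displacement falls from 87 to 58; Weeks 24 and 36 are unchanged.

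**Completers.** The Month 12 site visit is on Day 337 ± 3 (334-340). Adding 25 to 31 days gives Days 359-371, always inside 295-378. The scheduled Week 48 exam is then used. If it is missing, the follow-up exam becomes the Week 48 value.

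**Subjects.** The documents give no distribution of stopping times. Assume the 10% drop-out/non-evaluable rate (Protocol 11.1) is all early stopping, spread evenly: 0.10 × 150 = 15 subjects; 15 × 0.42 = 6.3 and 15 × 0.62 = 9.3, or about 6 to 9.

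**The case against.** The strongest reply is that Table 2 does not cover the follow-up exam. Its heading names Months 3, 6, 9 and 12, SAP 3.3 mentions Week 52 separately, and SAP 5.5 stops the endpoint at Week 48. On that reading nothing is mislabelled. The reading is fair, but the SAP never states it. SAP 7.3 assigns recorded data to windows, and the general exclusion in SAP 7.2 concerns unscheduled data, which this visit is not.

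A second reply is that findings are not lost. Nurses report any change in status to the investigator (Protocol 9.3.3), adverse events are collected through follow-up (SAP 11.1.1), and all data are listed by subject and visit (SAP 7). This stands and limits the point to the shift table.

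A third is that under Protocol 11.5 a better follow-up exam could not replace a worse EOT exam. That is true of displacement. It leaves the 112 only-record days as they are, and a worse follow-up exam could then replace even a completer's Week 48 exam. SAP 3.3 uses a different rule in any case.

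A reader might also infer that the on-treatment lesion rate is biased downwards. The documents do not support that as a fact. The regression is a dog finding, and Protocol 4.4.1 reports no unusual dermal findings in people treated for up to 3 months.

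**Conclusion.** The point holds as a minor defect in a safety table. Followed literally, SAP 3.3 can label an off-drug exam as a Week 12, 24, 36 or 48 result, for 60% of possible early EOT days in the base case (42-62% across variants). The percentages are shares of possible EOT days, not of subjects. The figure of 6 to 9 subjects rests on even timing, covers all three arms including placebo, and takes no account of those who withdraw consent and so have no follow-up exam.

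Three stronger readings are not supported. Not every early discontinuer is affected: 52 + 39 + 42 = 133 of 332 days (40%) produce no misplaced exam. The number affected is not 15, which counts every drop-out. And the lack of a follow-up row for completers is not in itself an error, since it agrees with the endpoint's definition through Week 48; SAP 11 also allows unspecified data to be summarized through follow-up. For completers the labelling risk arises only when the Week 48 exam is missing. The primary and other efficacy analyses are not involved.

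**What to change.** In SAP 3.3, state that the follow-up (EOT + 4 weeks) body-system exam is never assigned to the Week 12-48 windows. Do this by closing those rows to body-system exams later than the EOT site visit plus the 7-day nurse-visit allowance, and tabulate the exam in a separate Follow-up row. The earliest planned follow-up is EOT + 25 days, beyond EOT + 7, so the misassigned days fall from 199 to 0.

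The cut-off should run from the EOT site visit, not from the last dose. Protocol 9.3.1 ties the allowance to the site visit, and Protocol 7.6 asks only that an early EOT visit take place as soon as possible after stopping. With a site visit 3 days after the last dose and a nurse exam 7 days later, the EOT exam falls on day 3 + 7 = 10 and would be lost under a 7-days-after-dose rule.

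Also reconcile the closest-record rule in SAP 3.3 with the worst-record rule in Protocol 11.5, and record any departure in SAP 1.1. The cost is a few SAP sentences, one more table row and slightly fewer records in the on-treatment rows.

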## 4 ANALYSIS POPULATIONS

### 4.1 Safety Population

The safety population will include all enrolled subjects who receive at least one dose of study medication. Group assignment will follow actual treatment received. All safety analyses will be conducted using the safety population.

#### **4.2 Modified Intent-to-Treat Population**

The modified intent-to-treat (MITT) population will include all enrolled subjects who receive at least one dose of study medication. Group assignment will follow treatment group assigned at randomization. The primary efficacy analysis will be conducted using the MITT population.

#### **4.3 Per Protocol Population**

The per protocol (PP) population will consist of all subjects in the MITT population who do not have major protocol deviations considered to affect the primary efficacy variable DRSS, have completed their 48-week visit on treatment, and have been at least 70% compliant. The rules for determining exclusion from the per-protocol population will be made and implemented prior to unmasking. Sensitivity analyses of the primary efficacy variables will be conducted using the PP population.

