7.5 Replacement of Subjects

Subjects withdrawn for reasons other than lack of efficacy (treatment for PDR or DME) may be replaced.

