8.4.3 Treatment of PDR or DME

Criteria for treatment of PDR or DME in the study eye or qualified fellow eye during the study are summarized in [Appendix B](#). Treatment of PDR or DME in a non-qualified fellow eyes is at the discretion of the Investigator. Treatment will be recorded on the appropriate CRFs.

Subjects who receive treatment for PDR or DME in a study eye or qualified fellow eye may discontinue study medication at the discretion of the Investigator and subject. Subjects who remain in the trial will continue study medication.

The following scenarios apply depending on eye being treated for PDR or DME.

- For a study eye or qualified fellow eye requiring treatment, the Sponsor Medical Monitor should be informed prior to initiation of treatment. Additionally,
 - If the subject will discontinue study medication, the subject should undergo all EOT (Month 12/Early Withdrawal assessments (See [Section 9.3.2.16](#)) as soon as possible after study medication is stopped. EOT procedures should be conducted **prior** to treatment for PDR or DME in the study eye or qualified fellow eye. Treatment for PDR or DME will be in accordance with criteria in [Appendix B](#); following treatment, the subject will enter the 1-month Follow-up period.
 - If the subject will continue study medication, consult the Sponsor Medical Monitor to determine appropriate ocular assessments to be conducted prior to treatment for PDR or DME. Treatment for PDR or DME will be in accordance with criteria in [Appendix B](#).
- For a non-qualified fellow eye requiring treatment:
 - The subject will remain in the study and study assessments will be conducted per protocol prior to any treatment for PDR or DME. Treatment for PDR or DME in a non-qualified fellow eye is at the discretion of the Investigator.

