11.2.2.2 Per Protocol Population

The per protocol (PP) population will consist of all subjects in the MITT population who do not have major protocol deviations considered to affect the primary efficacy variable DRSS, have completed a minimum of 12 months of treatment and have been at least 70% compliant. Sensitivity analyses of the primary efficacy variables will be conducted using the PP population.

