### 7.2 Descriptive Statistics

For continuous variables, descriptive statistics will include the number of subjects (n), mean, standard deviation (SD), median, minimum and maximum. Categorical variables will be summarized using absolute and relative frequencies (i.e., counts and percentages). For categorical analyses, eyes that receive rescue therapy will be considered as treatment failures. Safety and PK data will be analyzed as collected.

All efficacy data will be summarized by treatment groups and overall using appropriate descriptive statistics. Summaries will be presented for both the MITT and PP populations, where applicable. Due to the small number of subjects enrolled at each center, all summaries and analyses will be performed using data pooled across centers. Unscheduled data, such as information from unscheduled visits or investigator comments, will be included in the data listings. In general, these data will be excluded from the summary tables unless otherwise specified.

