## **8 DISPOSITION AND EXIT STATUS**

### **8.1 Subject Disposition**

Subjects who are enrolled, complete the study, discontinue study medication, or withdraw from the study including reasons for study medication discontinuation or study withdrawal will be summarized along with the number and percentage of subjects in each of the analysis populations (safety, PP, PK and sub-study) in tabular format by treatment group and for all subjects. The number and percentage of subjects who completed 1-month follow-up visit will be summarized in the Safety population. The reasons for active treatment period discontinuation that will be summarized include: adverse events, treatment for PDR or DME, subject withdrew consent, lost to follow-up, protocol deviation, termination of study and other. Individual subject disposition data will be listed.

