## **10.1 Primary Efficacy Endpoint Analysis**

The primary hypotheses to be tested is that AKB-9778 15 mg twice daily and AKB-9778 15 mg once daily will be superior to placebo in the improvement of DR as measured by the ETDRS severity scale change from baseline at 48 weeks. Specifically, the primary endpoint is the percentage of subjects with an improvement in study eye severity of DR (ETDRS DRSS) of  $\geq 2$  steps at 48 weeks without need for treatment of PDR or DME (by IVT, laser, or vitrectomy) in the study eye. DRSS scores used for all analyses will be obtained from final adjudicated grading by the central reading center (Fundus Photograph Reading Center for the standard field images).

The primary hypotheses will be tested in the MITT population using a Fisher's Exact Test with a 2-sided 5% significance level. AKB-9778 15 mg twice daily will be tested first. If this is found to be statistically significant, then AKB-9778 15 mg once daily will be tested for statistical significance, at the same significance level. Cochran-Mantel-Haenszel (CMH) test stratified for baseline ETDRS DRSS (levels 4, 5 and 6) will also be used for testing primary hypothesis in the MITT population. Missing data will be imputed using LOCF; baseline values will not be carried forward.

As a sensitivity analysis, primary hypothesis will be tested using Fisher's Exact test, and CMH test stratified for baseline ETDRS DRSS (levels 4, 5 and 6) on OC in the PP population.

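### The per-protocol set drops study-eye rescue failures who stopped drug but can keep identical failures who continued, so the named sensitivity analysis is selected on outcome

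*SAP*

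**What the plan says.** **Who is in PP.** SAP 4.3 takes MITT subjects without relevant major deviations who "have completed their 48-week visit on treatment, and have been at least 70% compliant". Protocol 11.2.2.2 words the same restriction as subjects who "have completed a minimum of 12 months of treatment and have been at least 70% compliant". SAP 8.4 tabulates failure to complete as a reason for exclusion from PP. Neither document exempts a subject who stopped because of rescue. SAP 4.3 leaves the exclusion rules to be settled before unmasking.

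**How rescue counts.** SAP 10.1 defines response as improvement of at least 2 steps "without need for treatment of PDR or DME (by IVT, laser, or vitrectomy) in the study eye". SAP 7.2 adds: "For categorical analyses, eyes that receive rescue therapy will be considered as treatment failures". Protocol 7.5 treats rescue as lack of efficacy: "Subjects withdrawn for reasons other than lack of efficacy (treatment for PDR or DME) may be replaced". SAP 7.1 carries the last pre-rescue data forward even in observed-case (OC) analyses.

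**Who stops drug.** Under Protocol 8.4.3, subjects treated for PDR or DME in a study eye or qualified fellow eye "may discontinue study medication at the discretion of the Investigator and subject". Protocol 7.6 and Appendix B say the same. SAP 8.1 expects this route and lists among its discontinuation reasons "treatment for PDR or DME, subject withdrew consent, lost to follow-up".

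**Which analyses use PP.** The only analysis that SAP 10.1 labels a sensitivity analysis is Fisher's exact test and the CMH test on OC in PP. SAP 10 also lists the primary outcome for MITT and PP, each with LOCF and OC.

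**The concern.** The plan treats study-eye rescue as failure throughout and takes care to keep rescued eyes in the OC analysis. The completion clause in SAP 4.3 then removes some of those same failures. The carry-forward rule in SAP 7.1 cannot bring them back, because it acts only on subjects already in the analysis set.

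Which failures are removed depends on a choice made after randomisation and prompted by the outcome. Two subjects whose study eyes are rescued at the same time are both non-responders. The one who continues drug to Week 48 can be in PP; the one who stops cannot. The PP response rate is therefore conditional on not having failed and stopped. If stopping after rescue differs between arms, the PP comparison shifts for reasons unrelated to response, and agreement between PP and MITT is weaker reassurance than it appears.

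**Working it through.** **Inputs.** From SAP 3.1: response rates of 30% (active) and 5% (placebo), 45 evaluable and 50 planned per arm, 10% drop-out or non-evaluable, two-sided Fisher's exact test at 5%. The number of rescued stoppers per arm, r, is not in the documents. I assume 3 to 6 (6% to 12% of 50).

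**The plan's own figures.** Exact power of Fisher's test with 45 per arm at 30% against 5% is 86.3%, in line with the stated figure of above 85%. Then 45/(1 − 0.10) = 50 per arm. Both reproduce, and neither is in dispute.

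**Which clause removes the subjects.** SAP 8.2 counts expected doses only up to the last dosing date, so an early stopper can still reach 70% compliance. The completion clause does the removing.

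**Effect on the rates.** Removing r non-responders changes an arm's rate from x/n to x/(n − r), which is higher whenever x > 0. Expected responders are 0.30 × 50 = 15 and 0.05 × 50 = 2.5.

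- Active: 15/47 = 31.9% (r = 3); 15/44 = 34.1% (r = 6).
- Placebo: 2.5/47 = 5.3% (r = 3); 2.5/44 = 5.7% (r = 6).

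| Removal | Difference, r = 3 | Difference, r = 6 |
|---|---|---|
| None | 25.0 points | 25.0 points |
| Equal in both arms | 26.6 | 28.4 |
| Active only | 26.9 | 29.1 |
| Placebo only | 24.7 | 24.3 |

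**Effect on the test at the planned rates.** Rounding placebo to 3/50, 15/50 against 3/50 gives p = 0.0033. Removing 6 per arm gives 15/44 against 3/44, p = 0.0029. The conclusion does not change.

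**Effect on a borderline result.** Take 10/50 against 3/50, p = 0.071 with all failures kept.

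| Removed (active / placebo) | Table | Fisher p |
|---|---|---|
| 3 / 0 | 10/47 v 3/50 | 0.037 |
| 5 / 2 | 10/45 v 3/48 | 0.036 |
| 5 / 5 | 10/45 v 3/45 | 0.069 |
| 2 / 5 | 10/48 v 3/45 | 0.072 |
| 0 / 5 | 10/50 v 3/45 | 0.076 |

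In these cases p falls below 0.05 only when the active arm loses more failures than placebo. Equal removal barely moves it, and heavier loss on placebo raises it slightly.

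**The case against.** The strongest reply is that no decision rests on PP. The confirmatory test is in MITT, which keeps every dosed subject and counts rescued eyes as failures. MITT on OC is also listed in SAP 10 and keeps the rescued stoppers with pre-rescue data. Restricting PP to on-treatment completers is a common definition, both documents state it, and SAP 4.3 leaves the detailed exclusions to a masked later step. All of this stands and limits the weight of the point. It does not remove it: MITT on OC is not labelled a sensitivity analysis in SAP 10.1, and the text as it stands contains no exemption to apply at the later step.

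A reader might infer that the rule flatters the drug. The documents do not support that. If the drug works, more rescued stoppers on placebo is a natural pattern, and the difference then narrows slightly. A reader might also infer that all rescued subjects are lost from PP. Those who stay on drug can remain as failures.

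The assumed counts have no anchor in the documents. The upper value of 6 per arm exceeds the planned allowance of 5 per arm (10% of 50), although rescued subjects need not all fall within that allowance. The borderline example was chosen because it sits near 0.05.

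**Conclusion.** The point holds for the PP sensitivity analysis only. As written, SAP 4.3 removes known non-responders through a discretionary decision linked to the outcome, which conflicts with how SAP 7.1, 7.2 and 10.1 treat rescue. The primary MITT analysis is unaffected.

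The size is modest at the planned rates. With an assumed 3 to 6 rescued stoppers in one or both arms, the 25-point difference moves to between 24.3 and 29.1 points in the scenarios computed, in a direction that depends on which arm loses more. A nominal change of significance needs a result already close to 0.05 and heavier loss from the active arm. The change is worth making because it is cheap, not because the trial's conclusion depends on it.

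**What to change.** Before unmasking, add to SAP 4.3 that subjects who stopped study drug because the study eye was treated for PDR or DME stay in PP as non-responders, provided they were at least 70% compliant up to stopping and had no other major deviation. Keep the completion rule for every other reason, including treatment of a fellow eye only.

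The reason category in SAP 8.1 does not name the eye, and Protocol 8.4.3 also allows stopping after treatment of a qualified fellow eye. These subjects must therefore be identified by linking the disposition reason to the treatment CRF for the study eye. Protocol 8.4.3 already requires that treatment to be recorded.

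SAP 1.1 now states that there is no change from the protocol. It should record this departure from Protocol 11.2.2.2.

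The cost is a sentence in SAP 4.3, an entry in SAP 1.1 and one data linkage. The downside is that PP is no longer strictly a set of on-treatment completers. Rescue and stopping rules are not changed.
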